5.7 Study Oversight

Primary oversight during the conduct of the study will be the responsibility of the Principal Investigators at each Study Site. The Principal Investigators are responsible for communicating any issues that may compromise subject safety to the Sponsor's blinded Medical Monitor.

5.8 Safety Review Committee

5.8.1 General Safety Monitoring

Results of the SAD study performed with UPB-101 were reported in Section 1.4.1. In that clinical study, UPB-101 was safe and well-tolerated. Since the highest dose administered in the completed single-dose Phase 1 was [redacted] mg/kg (the equivalent of approximately [redacted] mg), all 3 doses proposed for Cohort 1 ([redacted]) and Cohort 2 ([redacted]) as well as the 2 doses of Cohort 3 ([redacted]) in the current study are supported by those data. However, the SRC will meet before the first subject in any cohort with [redacted] dosing receives their third dose as an extra precaution so as to assure that formal reviews of all the available safety data occur at specific timepoints in the study.

Part A: Subjects in Cohorts 1 and 2 will receive 3 doses of study drug. Before the first subject in each of those cohorts receives their third dose, the SRC will be convened. The committee will review at each of the 3 meetings the safety data available at that point in time from all enrolling cohorts. Subjects enrolled in Cohort 3 will receive 2 doses of the study drug. Therefore, no SRC meetings will be directly linked to the progress of those cohorts. The blinded safety data reviewed will include AEs, vital signs, physical examinations, ECGs, haematology, biochemistry, urinalyses, as well as subject withdrawals and replacements. Eosinophil data will not be sent to sites or reviewed by the SRC. Following this data review, the SRC will report their safety findings and make a recommendation whether the third dosing in the current cohort should proceed as planned or be modified (e.g., repeated or reduced), paused, or halted (Section 5.9 and Section 4.11).

Part B: Study drug exposures in Cohorts 4 and 5 will not exceed the exposure of any of the cohorts in Part A. If a [redacted] dosing regimen is selected for Cohorts 4 or Cohort 5 an SRC meeting will be convened prior to the first subject in the relevant cohort(s) receiving their third dose. The data to be reviewed, and the process for the SRC to report their safety findings, will be as those detailed for Part A above.

The data will be blinded for review; however, if considered necessary, the SRC can request that data be unblinded for either individual subjects or the entire dose cohort. The randomization code will be broken following tranScrip's standard procedures.

The SRC will be comprised of individuals with expertise in internal medicine, clinical development, allergy and clinical immunology, clinical pharmacology, safety risk management, and clinical operations. The SRC will include Sponsor (Upstream Bio) personnel, the Principal Investigators (their designees), and external experts.

The SRC will consist of voting members (the chairperson and additional members) and non-voting members. Blinded voting members will be the following:

- Principal Investigators (or their designates) from each of the Study Sites.
- tranScrip's (the study clinical contract research organisation [CRO]) Head of Translational Medicine/Clinical Pharmacology.
- tranScrip's Clinical Development Team Lead – Chairperson.

The following non-voting members will support the SRC voting members in their role:

- Sponsor's unblinded Medical Monitor.
- tranScrip study statistician (blinded).

Other non-voting members may be added as needed to support the SRC.

All voting members will constitute a quorum. Any SRC recommendation will be made by a unanimous quorum vote at a meeting. Non-voting members cannot vote for cohort progression, study termination, or study enrolment halt. In an exceptional circumstance (e.g., illness or sudden unavailability), the Chairperson will have the discretion, in consultation with the SRC, to have a SRC recommendation made in the absence of a maximum of 1 voting member.

5.8.2 PK Safety Monitoring

When subjects enrolled in each cohort have completed their respective Day 22 procedures, serum PK samples collected following the first dosing will be assessed in a timely fashion for UPB-101 concentrations (PK). The PK results will be analysed, and a summary report will be written by the Sponsor's PK consultant with particular attention to C_{max} and AUC_{tau} , with a comparison to the pre-study PK modelling as described in Section 5.10. The report will be distributed to all members of the SRC. Unblinding individual subject PK data will not be included in this report so as not to unblind the blinded members of the SRC. After reviewing the summary safety, any member of the SRC may request a formal meeting of that committee to discuss the results.

5.9 Stopping Criteria

5.9.1 Study Stopping Criteria

If any of the following events develop during the study, at any dose of UPB-101, and these events are considered by the Investigator and/or Sponsor to be at least probably related to the administration of UPB-101, an *ad hoc* SRC meeting will be called immediately to investigate the event and to provide a recommendation for stopping or continuing the study or modifying the protocol:

- One or more subjects develop an SAE.
- Two or more subjects in the same cohort develop severe non-serious AEs, independent of within or not within the same system-organ-class.
- One or more subjects develop elevated plasma concentrations of ALT or AST ≥ 3 -fold the ULN and elevated plasma concentrations of total bilirubin (TBL) ≥ 2 -fold the ULN which is confirmed by repeat testing at least 48 to 72 hours after the initial test.

If the SRC recommends modifying the protocol as a condition for restarting the study, a protocol amendment will be submitted to the relevant regulatory authorities and IEC.

Procedures required prior to restarting a halted study are listed in Section 5.11.

Dose Escalation Stopping Criteria

If any of the following events develop during the study, dose escalation will be halted and the SRC will review the event and make a recommendation to stop dose escalation and/or continue dosing with modifications:

- Two or more subjects administered UPB-101 have an elevated plasma concentration of ALT or AST $\geq 3 \times$ ULN that is considered by the Investigator and/or Sponsor related to the investigational product and is confirmed by repeat testing 48 to 72 hours after the initial test.
- Two or more subjects administered UPB-101 have an elevated plasma concentration of TBL $\geq 2 \times$ ULN that is considered by the Investigator and/or Sponsor related to the investigational product and is confirmed by repeat testing 48 to 72 hours after the initial test.
- For additional information on hepatic parameter abnormalities, refer to Appendix 1, Liver Safety Monitoring and Assessment.
- One or more subjects administered UPB-101 has prolongation of QTcF, defined as QTcF >500 ms or >60 ms change from Baseline, that, on multiple ECGs, persists for at least 30 minutes and is considered by the Investigator and/or Sponsor related to the investigational product.
- Pharmacokinetic Stopping Rules – see Section 5.10.
- One or more subjects administered UPB-101 develop any other event that poses an unacceptable risk to other subjects in the study.

Procedures required prior to restarting a halted study are listed in Section 5.11.

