5.4.5 Electrocardiogram

Electrocardiograms will be conducted on visit days detailed in Table 4 through Table 9 in Section 3.3. A standard 12-lead ECG will be recorded after the subject has been supine for at least 5 minutes. All ECGs will be acquired in triplicate with a maximum of 5 minutes between the first and the third recordings. All recordings will be transmitted to the central ECG laboratory for interval calculations and interpretation.

The Investigator or designated physician will review all ECGs and opine regarding the tracings. A paper printout of every ECG will be stored at the site.

All ECG will include at a minimum the subject's study number as well as the time and date of each recording. On dosing days, ECGs will be conducted within 60 minutes pre-dose and approximately 2 hours post-dose (see Table 9). ECG assessments will be performed prior to any scheduled blood tests, FeNO measurements, and/or study drug administration.

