12 APPENDICES

Appendix 1 Liver Safety Monitoring and Assessment

Any subject enrolled in a clinical study with active drug therapy that reveals an increase of serum aminotransferases $\geq 3 \times$ ULN or bilirubin $\geq 2 \times$ ULN should undergo detailed testing for liver enzymes using the study Chemistry panel defined in Table 10 which includes ALT, AST, alkaline phosphatase (ALP) and TBL. Testing should be repeated within 48 to 72 hours of notification of the test results. For studies for which a central laboratory is used, alerts will be generated by the central laboratory to inform the Investigator, Sponsor's Medical Monitor, and study team when ALT, AST or TBL exceed the thresholds above. Subjects should be asked if they have any symptoms suggestive of hepatobiliary dysfunction.

Definition of Liver Abnormalities

Confirmed abnormalities will be characterized as moderate or severe by the Investigator where ULN:

	ALT or AST	TBL
Moderate	$>3 \times$ ULN	or
Severe†	$>3 \times$ ULN	and

† Hy's Law Definition: Drug-induced jaundice caused by hepatocellular injury, without a significant obstructive component, has a high rate of bad outcomes, from 10% to 50% mortality (or transplant). The 2 “requirements” for Hy’s Law are:

- Evidence that a drug can cause hepatocellular-type injury, generally shown by an increase in transaminase elevations higher than $3 \times$ ULN (“ $2 \times$ ULN elevations are too common in treated and untreated subjects to be discriminating”).
- Cases of increased bilirubin (at least $2 \times$ ULN) with concurrent transaminase elevations at least $3 \times$ ULN and no evidence of intra- or extra-hepatic bilirubin obstruction (elevated ALP) or Gilbert’s syndrome (Temple 2006).

In addition, the subject should be considered to have severe hepatic abnormalities for any of the following:

- ALT or AST $>8 \times$ ULN.
- ALT or AST $>5 \times$ ULN for more than 2 weeks.
- ALT or AST $>3 \times$ ULN and International Normalized Ratio (INR) >1.5 (If INR testing is applicable/evaluated).

- ALT or AST $>3 \times$ ULN with the appearance of fatigue, nausea, vomiting, right upper quadrant pain or tenderness, fever, rash and/or eosinophilia ($>5\%$).

The Investigator may determine that abnormal liver test results, other than as described above, may qualify as moderate or severe abnormalities, and require additional monitoring and follow-up.

Follow-up Procedures

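### The liver retest that Appendix 1 tells sites to take is not ensured to count as confirmation under the stopping criteria in Protocol Section 5.9.1

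*Protocol*

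**What the plan says.** Three places in the protocol time the confirmatory liver test.

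- **Section 5.9.1, Dose Escalation Stopping Criteria.** There are two liver criteria, one for ALT or AST at 3 × ULN or more and one for total bilirubin at 2 × ULN or more. Each needs two or more subjects, a judgement of relatedness, and an elevation that is "confirmed by repeat testing 48 to 72 hours after the initial test".
- **Section 5.9.1, study stopping.** One or more subjects with both elevations together, "which is confirmed by repeat testing at least 48 to 72 hours after the initial test".
- **Appendix 1.** At the same thresholds, "Testing should be repeated within 48 to 72 hours of notification of the test results". Where a central laboratory is used, "alerts will be generated by the central laboratory to inform the Investigator", along with the medical monitor and study team. No turnaround time is given.

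The dose-escalation list refers the reader to Appendix 1 for more on hepatic abnormalities, but does not say which timing governs.

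On QTcF, the dose-escalation list asks for prolongation "that, on multiple ECGs, persists for at least 30 minutes". Section 5.4.5 says "All ECGs will be acquired in triplicate with a maximum of 5 minutes between the first and the third recordings". Table 9 schedules one ECG set before dosing and one at 2 hours after.

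The SAP does not restate the stopping criteria. Its Section 6.4 leaves the remit of the Safety Review Committee (SRC) to a charter that is not among the documents.

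**The concern.** One retest is described with two starting points and three windows. Appendix 1 is the only text that instructs a site to take it, so a site will schedule the sample from the notification date. Section 5.9.1 then judges that sample by its distance from the initial test. Any delay between sample and notification separates the two clocks.

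Safety is the primary objective, and these criteria decide whether escalation halts and the SRC reviews. Under Section 5.11, a restart after a halt needs written regulatory approval through a substantial amendment. With that consequence, sites and the SRC need a single reading of when an elevation is confirmed. As written, the same subject can be confirmed or unconfirmed depending on which passage is applied.

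**Working it through.** The plan states no figure to reproduce, so the check is interval arithmetic.

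**Inputs.** The confirmation window for the dose-escalation criteria is 48–72 h after the initial test (Section 5.9.1). The retest window is tied to notification, with limits of 48 and 72 h (Appendix 1). The lag L, from initial sample to notification, is not in the documents and is assumed here over 0–72 h. The initial test is taken as the time of the first sample.

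**Could a scheduled visit supply the retest instead?** The closest pair of post-dose chemistry visits in Tables 5 to 8 is Day 29 (±2) and Day 36 (±1). They are nominally 7 days apart, and at the edges of their windows 35 − 31 = 4 days, or 96 h. That is beyond 72 h, so confirmation rests on the Appendix 1 retest or on an unscheduled sample.

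**Reading A: 48–72 h after notification.** The retest falls L + 48 to L + 72 h after the initial test. Its overlap with 48–72 h is max(0, 24 − L) hours, so the qualifying share is (24 − L)/24.

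**Reading B: any time up to 72 h after notification.** The retest falls L to L + 72 h after the initial test. For L up to 48 h the overlap is 24 h, a share of 24/72 = 1/3. The share falling before 48 h is (48 − L)/72.

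| Assumed L (h) | A: retest (h) | A: share in 48–72 h | B: retest (h) | B: share in 48–72 h | B: share before 48 h |
|---|---|---|---|---|---|
| 0 | 48–72 | 24/24 = 100% | 0–72 | 1/3 | 48/72 = 2/3 |
| 6 | 54–78 | 18/24 = 75% | 6–78 | 1/3 | 42/72 = 58% |
| 12 | 60–84 | 12/24 = 50% | 12–84 | 1/3 | 36/72 = 1/2 |
| 24 | 72–96 | 72 h point only | 24–96 | 1/3 | 24/72 = 1/3 |
| 36 | 84–108 | none | 36–108 | 1/3 | 12/72 = 1/6 |
| 48 | 96–120 | none | 48–120 | 1/3 | 0 |
| 72 | 120–144 | none | 72–144 | 72 h point only | 0 |

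The shares are fractions of the permitted time, not probabilities.

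**Study-stopping criterion.** Take its minimum as 48 h. Under reading A the retest is never earlier than L + 48, so the criterion is satisfied at every lag. Under reading B it can be missed: with L = 12 h and a retest 24 h after notification, the sample is 12 + 24 = 36 h after the initial test.

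**QTcF.** One triplicate covers at most 5 minutes, against the 30 required. In Table 9 the pre-dose set (−60 ± 15 min) and the post-dose set (120 ± 30 min) are between 90 − (−45) = 135 and 150 − (−75) = 225 minutes apart. After the first dose only the 2-hour set follows drug that day, and Table 5 next lists an ECG on Day 4. Section 3.3 allows repeats for safety but names no trigger or interval.

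**The case against.** A reader might infer that the plan's procedures cannot produce a confirming liver test, so that these criteria cannot be met. The documents do not support that. Under reading A the windows overlap at lags below 24 h, and under reading B some retest time satisfies both texts at any lag below 72 h. The study-stopping criterion, with its minimum taken as 48 h, accepts every retest taken 48–72 h after notification. A complete mismatch needs both the narrow reading of Appendix 1 and an assumed lag above 24 h.

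There are also other routes to review. The dose-escalation list ends with a catch-all for events posing unacceptable risk. A single SAE judged at least probably related calls an ad hoc SRC meeting, and severe hepatic abnormalities may be reported as SAEs. Laboratory alerts go out before any retest.

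These points limit the concern but do not remove it. Overlap shows that a qualifying retest is possible, yet no text tells the site to aim for the common part. The catch-all and SAE routes rest on judgement and do not settle whether a defined criterion is met. An alert informs but does not confirm.

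A reader might likewise infer that the QTcF criterion cannot be met from the ECGs taken. That is not supported either. Safety repeats are allowed, subjects stay at least 4 hours after dosing, and at later dosing visits the two scheduled sets are more than 30 minutes apart with both following earlier drug. A rule that asks for multiple ECGs also implies repeating an abnormal one. What is missing is only an explicit requirement to repeat.

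**Conclusion.** The point holds as a failure to ensure confirmation, mainly for the two dose-escalation liver criteria. The difference in starting point is plain on the page and needs no assumption. Its effect depends on an unstated lag. Under reading A, half the retest window qualifies at 12 h, one point at 24 h, and nothing beyond that. Under reading B, one third qualifies for lags up to 48 h, and at lags below 48 h a retest may come too early for the study-stopping criterion as well. That criterion's minimum, stated as a range, is unclear in itself.

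The documents do not show that a criterion would be missed in practice, because they give neither the turnaround time nor the SRC charter. The QTcF wording is a secondary clarification and would not stand as a finding alone.

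**What to change.** Reconcile Section 5.9.1 and Appendix 1 so that the same starting point (initial test or notification) and the same window apply to the dose-escalation criteria, the study-stopping criterion and the site instruction. State the window so that it has one reading, replacing both the minimum given as a range and the ambiguous *within*. Which starting point and window to use is for the sponsor's physicians.

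In the same amendment, reconcile the QTcF persistence wording with Section 5.4.5 and Table 9, so that it is clear whether and how a repeat ECG is obtained. No clinical limit or rule is proposed here.

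The cost is amendment wording and a notice to sites. Reconciling the liver timing changes no scheduled visit, sample size or SAP analysis.

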5.10 Pharmacokinetic Stopping Limits

UPB-101 exposure at the NOAEL dose (█ mg/kg IV) in the 26-week cynomolgus monkey study gave a C_{max} █ $\mu\text{g}/\text{mL}$ and AUC_{tau} █ $\mu\text{g} \cdot \text{day}/\text{mL}$, which are █-fold and █-fold higher than the predicted C_{max} and AUC_{tau} at the maximum dose (█ mg SC) in the current study, which are █ $\mu\text{g}/\text{mL}$ and █ day. $\mu\text{g}/\text{mL}$, respectively (see Section 1.7).

Despite the very large margins, if the following events develop during the study, the SRC will review the data and make a recommendation to stop dosing, continue dosing, or continue dosing with modifications: One or more subjects administered UPB-101 have C_{max} █ of the preclinical NOAEL level, i.e., C_{max} █ $\mu\text{g}/\text{mL}$.

Procedures required prior to restarting a halted study are listed in Section 5.11.

5.11 Re-starting the Clinical Study Following a Clinical Stop Due to a Stopping Rule

Should the clinical study be halted because of any stopping rule listed in Section 5.9 or 5.10 was triggered, the study restart will only be possible after receipt of written regulatory

authority approval via a substantial Clinical Trial Application amendment (with or without a protocol modification required by the SRC or Sponsor etc.).

6 STUDY EFFICACY ASSESSMENTS AND PROCEDURES

6.1 Pharmacodynamic Assessments

The assessments described in this section will be conducted to assess asthma-related PD biomarkers. Samples will be collected as indicated in Section 3.3; the actual date and time of each sample collection will be recorded in the eCRF. Blood sample collection, handling, and storage will be described in the specimen collection and processing instructions. Blood samples for biomarker analysis will be taken and frozen. The decision to assay the frozen samples will be based on results from earlier sample analyses.

On dosing days, all PD assessments must be completed prior to initiation of the study drug administration.

Numerous cytokines are involved in the pathogenesis of asthma and several additional biomarkers have been associated with asthma activity (Custovic, Siddiqui et al. 2022). Several approved or in development asthma medications target cytokines (Lambrecht, Hammad et al. 2019).

Plasma levels of IL-5, IL-13, IFN λ , IL-17A, eotaxin-3, IP-10 (C-X-C motif chemokine ligand 10), and TSLP will be measured using ultrasensitive assays. Tryptase, carboxypeptidase, and TARC will also be measured. CRP, and total IgE will be assayed by the central clinical laboratory.

Initially, select samples from those collected will be analysed and the resulting data assessed. Following this, should analysis of the remaining samples be deemed informative, they too will be analysed.

6.1.1 Fractional Exhaled Nitric Oxide

Measuring the FeNO level in asthmatic subjects is used as a surrogate marker for the presence and degree of airway inflammation. The FeNO levels will be measured via exhaled breath.

Subjects should refrain from eating nitrate-rich foods for at least 9 hours prior to FeNO measurements (see Section 4.8.3).

Assessment of FeNO will be conducted as detailed in Table 4 through Table 9 in Section 3.3.

6.1.2 Blood Eosinophils

Increased eosinophils are associated with increased severity, exacerbations, decreased lung function, and mortality in subjects with asthma (Hospers, Schouten et al. 2000, Garcia, Taille et al. 2013, Talini, Novelli et al. 2015, Price, Wilson et al. 2016). Blood eosinophils have become an established biomarker in inflammatory airway disease (Kostikas, Brindicci et al. 2018).

Absolute numbers of blood eosinophils will be measured using blood collected as part of the automated complete blood count clinical laboratory test which includes a differential count of white blood cells. Results will be reported at the highest precision (level of significant figures) offered by the clinical laboratory. Assessment of blood eosinophils will be conducted at the visits reflected in Section 3.3. The sites will be blinded to eosinophil count.

6.1.3 Total Immunoglobulin E

Total IgE is a well-established biomarker for severe asthma whose levels have been shown to be targeted and/or reduced by current biologic therapies (Lambrecht, Hammad et al. 2019). Total IgE levels will be measured as detailed in Table 4 through Table 9 in Section 3.3.

6.1.4 Flow Cytometry – pSTAT and Receptor Occupancy

Phosphorylated signal transducer and activator of transcription and receptor occupancy will be assayed via flow cytometry. Blood samples obtained from subjects will be analysed fresh or frozen. The decision to assay the frozen samples will be based on the results from the fresh samples. Analysis of blood samples (whether fresh or frozen) for pSTAT may be discontinued, based on assay status.

